### **5.3.2 Drug Concentration and Anti-Drug Antibody Measurements**

#### **5.3.2.1 Collection of Samples for Analysis**

##### **Blood Samples for Upadacitinib PK Assay**

Blood samples for assay of upadacitinib and possibly other medications will be collected as follows:

- At Weeks 2 and 4 prior to dosing;
- At Weeks 8, 12, 14, 18, 22, 26, 30, 36, 42 and 48/PD at any time during the visit.

On Week 2 and Week 4 visit days, if possible, subjects should take the oral study drug dose at the clinic after collecting the pharmacokinetic (PK) blood sample, except if the subjects regularly take the study drug dose at night. Those subjects who regularly take the oral study drug dose at night should continue to take oral study drug according to their normal schedule. For all other visits, subjects can take the oral study drug dose on visit days at their regular schedule and not necessarily at the clinic.

For all PK samples, the date and accurate time of the PK sample collection will be recorded on the lab requisition form. The date and accurate time of the last two study drug doses will be recorded on the eCRF to the nearest minute.

Refer to the study specific laboratory manual for detailed instructions on sample collection, processing, and shipment.

### **5.3.2.2 Measurement Methods**

Plasma concentrations of upadacitinib will be determined by the Drug Analysis Department at AbbVie using a validated liquid chromatography/mass spectrometry method.

### **5.3.3 Efficacy Variables**

#### **5.3.3.1 Period 1 Variables**

##### **5.3.3.1.1 Primary Variables**

The primary endpoint in Period 1 is the proportion of subjects achieving ACR20 response at Week 12 (US/FDA regulatory purposes) or the proportion of subjects achieving CR based on DAS28 (CRP) at Week 12 (EU/EMA regulatory purposes). Analyses will be conducted separately for US/FDA regulatory purposes and EU/EMA regulatory purposes; for each set of analysis, only one primary endpoint is specified.

ACR20 response rate will be determined based on 20% or greater improvement in TJC and SJC and  $\geq 3$  of the 5 measures of Patient's Assessment of Pain (VAS), Patient's Global Assessment of Disease Activity (VAS), Physician's Global Assessment of Disease Activity (VAS), HAQ-DI, or hsCRP.

CR is defined as DAS28 (CRP)  $< 2.6$ .

##### **5.3.3.1.2 Key Secondary Variables**

Ranked key secondary endpoints (upadacitinib versus placebo if not otherwise specified) for US/FDA regulatory purposes are:

1. Change from baseline in DAS28 (CRP) at Week 12;
2. Change from baseline in mTSS at Week 26;

3. Change from baseline in HAQ-DI at Week 12;
4. ACR50 response rate at Week 12 (non-inferiority of upadacitinib vs ADA);
5. Change from baseline in SF-36 Physical Component Score (PCS) at Week 12;
6. Proportion of subjects achieving LDA based on DAS28 (CRP)  $\leq 3.2$  at Week 12;
7. Proportion of subjects achieving CR based on DAS28 (CRP) at Week 12;
8. Proportion of subjects achieving LDA based on Clinical Disease Activity Index (CDAI) at Week 12;
9. Change from baseline in morning stiffness at Week 12;
10. Change from baseline in FACIT-F at Week 12;
11. ACR50 response rate at Week 12 (superiority of upadacitinib vs. ADA);
12. Change from baseline in Patient's Assessment of Pain at Week 12 (superiority of upadacitinib vs. ADA);
13. Change from baseline in HAQ-DI at Week 12 (superiority of upadacitinib vs. ADA).

Other key secondary endpoints (upadacitinib versus placebo) for US/FDA regulatory purposes are:

- ACR50 response rate at Week 12
- ACR70 response rate at Week 12
- Proportion of subjects with no radiographic progression (defined as change from baseline mTSS  $\leq 0$ ) at Week 26

Ranked key secondary endpoints (upadacitinib versus placebo if not otherwise specified) for EU/EMA regulatory purposes are:

1. Change from baseline in modified Total Sharp Score (mTSS) at Week 26;
2. Proportion of subjects achieving LDA based on DAS28 (CRP)  $\leq 3.2$  at Week 12;

3. Change from baseline in DAS28 (CRP) at Week 12;
4. Change from baseline in HAQ-DI at Week 12;
5. ACR20 response rate at Week 12;
6. Proportion of subjects achieving LDA based on DAS28 (CRP)  $\leq 3.2$  at Week 12 (non-inferiority of upadacitinib versus ADA);
7. Change from baseline in SF-36 PCS at Week 12;
8. Proportion of subjects achieving LDA based on Clinical Disease Activity Index (CDAI) at Week 12
9. Change from baseline in morning stiffness at Week 12;
10. Change from baseline in FACIT-F at Week 12.
11. Proportion of subjects with no radiographic progression (defined as change from baseline mTSS  $\leq 0$ ) at Week 26;

Other key secondary endpoints (upadacitinib versus placebo) for EU/EMA regulatory purposes are:

- ACR50 response rate at Week 12
- ACR70 response rate at Week 12

ACR20/50/70 response rates will be determined based on 20%/50%/70% or greater improvement in TJC and SJC and  $\geq 3$  of the 5 measures of Patient's Assessment of Pain (VAS), Patient's Global Assessment of Disease Activity (VAS), Physician's Global Assessment of Disease Activity (VAS), HAQ-DI, or hsCRP.

### **5.3.3.1.3 Additional Variables**

Additional endpoints (upadacitinib versus placebo and adalimumab) at all visits are:

- Change from baseline in individual components of ACR response;
- ACR20/50/70 response rates;

- Change from baseline in DAS28(CRP) and DAS28 (erythrocyte sedimentation rate [ESR]);
- Change from baseline in CDAI and SDAI;
- Proportion of subjects achieving LDA or CR based on DAS28 (CRP), DAS28 (ESR), Simplified Disease Activity Index (SDAI), and CDAI criteria (see below);
- Change from baseline in morning stiffness;
- Proportion of subjects with change from baseline in HAQ-DI  $\leq -0.22$ ;
- Proportion of subjects with change from baseline in HAQ-DI  $\leq -0.3$ ;
- ACR/EULAR Boolean remission.

	DAS28 (CRP) and DAS28 (ESR)	SDAI	CDAI
LDA	$\leq 3.2$	$\leq 11.0$	$\leq 10$
CR	$< 2.6$	$\leq 3.3$	$\leq 2.8$

Additional endpoints at Weeks 12, 26, and 48 are:

- Change from baseline in SF-36;
- Change from baseline in FACIT-F.
- Change from baseline in RA-WIS.
- Change from baseline in EQ-5D-5L.

Additional endpoints at Weeks 26 and 48 are:

- Change from baseline in modified Total Sharp Score (mTSS);
- Proportion of subjects with no radiographic progression (defined as change from baseline in mTSS  $\leq 0$ );
- Change from baseline in joint space narrowing score and joint erosion score.

### 5.3.3.2 Period 2 Variables

Assessments to evaluate efficacy of treatment in Period 2 will be analyzed for the following measures at Weeks 60, 72, 84, 96, and every 12 weeks thereafter until completion of the study:

- ACR20/50/70 response rates;
- Change from baseline in individual ACR components;
- Change from baseline in DAS28 (CRP);
- Change from baseline in DAS28 (ESR);
- Change from baseline in CDAI and SDAI;
- Change from baseline in morning stiffness;
- Proportion of subjects achieving LDA and the proportion of subjects achieving CR based on DAS28 (CRP), DAS28 (ESR), SDAI, and CDAI criteria (as defined for Period 1);
- Proportion of subjects with change from baseline in HAQ-DI  $\leq -0.22$ ;
- Proportion of subjects with change from baseline in HAQ-DI  $\leq -0.3$ ;
- Concomitant corticosteroid use (systemic use and intra-articular injections);
- ACR/EULAR Boolean remission.

Additionally, assessment for the evaluation of radiographic changes in Period 2 will occur at Week 96 and every 96 weeks thereafter (or Premature Discontinuation visit):

- Change from baseline in modified Total Sharp Score (mTSS);
- Proportion of subjects with no radiographic progression (defined as change from baseline in mTSS of  $\leq 0$ );
- Change from baseline in Radiographic joint space narrowing and erosion scores.

### **5.3.4 Safety Variables**

Safety evaluations include AE monitoring, physical examinations, vital sign measurements, ECG, and clinical laboratory testing (hematology, chemistry, and urinalysis) as a measure of safety and tolerability for the entire study duration.

### **5.3.5 Pharmacokinetic Variables**

Plasma upadacitinib concentrations will be obtained at the times indicated in [Table 2](#). A non-linear mixed-effects modeling approach will be used to estimate the population central values and the empirical Bayesian estimates of the individual values of upadacitinib oral clearance (CL/F) and volume of distribution (V/F). Additional parameters may be estimated if useful in the interpretation of the data.

### **5.3.6 Exploratory Research Variables and Validation Studies**

Optional samples may be collected to conduct exploratory investigations into known and novel biomarkers. The types of biomarkers to be analyzed may include, but are not limited to nucleic acids, proteins, lipids, or metabolites.

Biomarker assessments may be used to assess and generate prognostic, predictive, pharmacodynamic, or surrogate biomarker signatures. These assessments may be explored in the context of RA or related conditions and/or upadacitinib or drugs of similar classes. The results from these analyses are exploratory in nature and may not be included with the clinical study report (CSR).

The samples may also be used to develop new therapies, research methods or technologies. In addition, samples from this study may be stored for future use. Samples may then be used to validate putative biomarker signatures obtained from a prospective study, leading to the development of diagnostic tests.

## **5.4 Removal of Subjects from Therapy or Assessment**

### **5.4.1 Discontinuation of Individual Subjects**

Subjects can request to be discontinued from participating in the study at any time for any reason, including but not limited to disease progression or lack of response to treatment. The Investigator may discontinue any subject's participation for any reason, including an AE, safety concerns, lack of efficacy, or failure to comply with the protocol. See Section 6.1.7 for toxicity management criteria.

Subjects will have study drug treatment discontinued immediately if any of the following occur:

- Clinically significant abnormal laboratory results or AEs, which rule out continuation of the study drug, as determined by the Investigator or the AbbVie Therapeutic Area Medical Director.
- Serious infections (e.g., sepsis) which cannot be adequately controlled within 2 weeks by anti-infective treatment or would put the subject at risk for continued participation in the trial as determined by the Investigator.
- The Investigator believes it is in the best interest of the subject.
- The subject requests withdrawal from the study.
- Inclusion or exclusion criteria violation was noted after the subject started study drug, when continuation of the study drug would place the subject at risk as determined by the AbbVie Therapeutic Area Medical Director.
- Introduction of prohibited medications or dosages when continuation of the study drug would place the subject at risk, as determined by the AbbVie Therapeutic Area Medical Director.
- Subject is non-compliant with TB prophylaxis (if applicable) or develops active TB at any time during the study.
- The subject becomes pregnant while on study drug.
- Malignancy, except for localized NMSC or carcinoma in situ of the cervix.
- Subject is diagnosed with lupus-like syndrome, multiple sclerosis, or demyelinating disease.

- Subject is significantly non-compliant with study procedures which would put the subject at risk for continued participation as determined by the Investigator.
- Subject develops a gastrointestinal perforation.
- Subjects with disease progression or not responding to treatment are to be withdrawn from the trial based on investigator's discretion.
- Starting at Week 48, at least 20% improvement in BOTH TJC AND SJC compared to baseline is required to remain on study drug. Anyone who does not fulfill this criterion at 2 consecutive visits (starting at Week 48) must be discontinued from study drug.

In order to minimize missing data for efficacy and safety assessments, subjects who prematurely discontinue study drug treatment or study participation should complete a Premature Discontinuation visit (PD visit) as described in Section 5.1 (Overall Study Design and Plan: Description)

All attempts must be made to determine the date of the last study drug dose and the primary reason for discontinuation of study drug or study participation. The information will be recorded on the appropriate eCRF page. However, these procedures should not interfere with the initiation of any new treatments or therapeutic modalities that the Investigator feels are necessary to treat the subject's condition. Following discontinuation of study drug, the subject will be treated in accordance with the Investigator's best clinical judgment, irrespective of whether the subject decides to continue participation in the study.

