### **6.1.7 Toxicity Management**

The toxicity management of the AEs including AEs of special interest consists of safety monitoring (review of AEs on an ongoing basis, and periodical/ad hoc review of safety issues by a safety data monitoring committee), interruption of study drug dosing with appropriate clinical management if applicable, and discontinuation of the subjects from study drug. The management of specific AEs and laboratory parameters is described below.

For subjects who discontinued study drug but continued study participation and are instead on standard of care therapies, these toxicity management requirements do not apply (including alerts from the central lab) and any intolerability to standard of care therapies should be managed by the prescribing physician.

**Serious Infections:** Subjects should be closely monitored for the development of signs and symptoms of infection during and after treatment with study drug. Study drug should be interrupted if a subject develops a serious infection or an opportunistic infection. A subject who develops a new infection during treatment with study drug should undergo prompt diagnostic testing appropriate for an immunocompromised subject. As appropriate, antimicrobial therapy should be initiated, and the subject should be closely monitored. Re-challenge with study drug may occur once the infection has been successfully treated. If study drug has been interrupted for a serious infection for more than 14 consecutive days during the first 26 weeks, more than 21 days between Weeks 26 and 48 or more than 30 consecutive days thereafter, the subject must be discontinued from study drug. Subjects who develop active TB must be permanently discontinued from study drug.

**Gastrointestinal Perforation:** Subjects presenting with the onset of signs or symptoms of a serious gastrointestinal event should be evaluated promptly for early identification of

gastrointestinal perforation. If the diagnosis of gastrointestinal perforation is confirmed, the subject must be discontinued from study drug.

**Cardiovascular Events:** Subjects presenting with potential cardiovascular events should be carefully monitored. These events will be reviewed and adjudicated by an independent Cardiovascular Adjudication Committee in a blinded manner.

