**Malignancy:** Subjects who develop malignancy other than NMSC or carcinoma in-situ of the cervix must be discontinued from study drug. Information including histopathological results should be queried for the confirmation of the diagnosis.

**ECG Abnormality:** Subjects must be discontinued from study drug for an ECG change considered clinically significant and with reasonable possibility of relationship to study drug OR a confirmed absolute QTcF value > 500 msec.

**Management of Select Laboratory Abnormalities:** For any given laboratory abnormality, the Investigator should assess the subject, apply the standard of care for medical evaluation and treatment following any local guidelines. Specific toxicity management guidelines for abnormal laboratory values (confirmation by repeat testing is required) are described in [Table 7](#) and may require an appropriate supplemental eCRF be completed. All abnormal laboratory tests that are considered clinically significant by the Investigator will be followed to a satisfactory resolution. If a repeat test is required per [Table 7](#), the repeat testing must occur as soon as possible.

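### Protocol 5.4.1 and 6.1.7 set different mandatory stopping criteria for some serious infections after Week 26 and for non-localized NMSC, and neither says which prevails

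*Protocol*

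**What the plan says.** **Force of the list in Protocol 5.4.1.** The list opens with "Subjects will have study drug treatment discontinued immediately if any of the following occur". It is a mandatory list, not guidance.

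**Serious infection.** One item on that list is "Serious infections (e.g., sepsis) which cannot be adequately controlled within 2 weeks by anti-infective treatment". No study period is attached to the 2-week limit. The same bullet adds a second trigger that rests on the Investigator's view of risk.

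Protocol 6.1.7 begins with a hold: "Study drug should be interrupted if a subject develops a serious infection or an opportunistic infection". It then allows a restart: "Re-challenge with study drug may occur once the infection has been successfully treated". Its mandatory stop depends on the length of the hold and on the period: "If study drug has been interrupted for a serious infection for more than 14 consecutive days during the first 26 weeks", then "more than 21 days between Weeks 26 and 48 or more than 30 consecutive days thereafter, the subject must be discontinued from study drug".

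**Malignancy.** Protocol 5.4.1 lists "Malignancy, except for localized NMSC or carcinoma in situ of the cervix". Protocol 6.1.7 states: "Subjects who develop malignancy other than NMSC or carcinoma in-situ of the cervix must be discontinued from study drug". The word that limits the exemption to localized disease appears only in 5.4.1.

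**Link between the sections.** Section 5.4.1 sends the reader to 6.1.7 for toxicity management and then states criteria of its own. Neither section says which applies when they differ.

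**The concern.** Both sections are written as mandatory, and a subject can meet the stopping criterion in one and not in the other. Two sites could each follow the protocol text and treat the same event differently.

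Serious infections and malignancies of all types are adverse events of special interest in Protocol 6.1.1.3, so this is core safety text. Three kinds of result depend on who is taken off study drug:

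- **Discontinuation counts:** disposition by primary reason (SAP 7.0) and adverse events leading to discontinuation (SAP 10.2.1.1 and 10.2.2.1).
- **Protocol deviations:** Protocol 7.0 and SAP 6.4 count subjects who met a withdrawal criterion and were not withdrawn. A site that restarts drug as 6.1.7 permits could be recorded under that heading because of 5.4.1.
- **Some efficacy summaries:** those in which discontinuation of study drug changes how a subject's later data are handled.

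**Working it through.** The documents give no figure to reproduce here. The check sets the rules side by side and subtracts day limits.

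**Step 1. What each clock measures.** The 2 weeks in 5.4.1 run on control of the infection. The 14, 21 and 30 days in 6.1.7 run on the interruption of dosing. To compare them, assume that the hold starts on the day the 2-week clock starts; 5.4.1 does not say when its clock starts.

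**Step 2. Window with opposite instructions** = 6.1.7 limit minus 14 days.

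| Period | 6.1.7 limit on the hold | 5.4.1 limit on control | Difference | Hold lengths in conflict |
|---|---|---|---|---|
| First 26 weeks | 14 days | 14 days | 14 − 14 = 0 | none |
| Weeks 26 to 48 | 21 days | 14 days | 21 − 14 = 7 | days 15 to 21 |
| After Week 48 | 30 days | 14 days | 30 − 14 = 16 | days 15 to 30 |

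**Step 3. A worked case.** A serious infection starts at Week 30 and dosing is held at once. It is not adequately controlled at day 14 and is successfully treated by day 20. Under 5.4.1 the subject must be discontinued. Under 6.1.7 the hold is within 21 days and the restart condition is met.

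**Step 4. Cases outside the conflict.** If the infection is controlled within 14 days, the 2-week limit in 5.4.1 is not triggered, however long dosing is held. If the hold exceeds the 6.1.7 limit, 6.1.7 also requires a stop.

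**Step 5. NMSC.** Localized NMSC is exempt in both sections, so there is no conflict. Non-localized NMSC must stop under 5.4.1 and lies outside the mandatory stop in 6.1.7. This difference is not tied to a study period.

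**Step 6. Tracing the infection conflict into the efficacy analyses.**

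- The primary and ranked key secondary endpoints are at Week 12 or Week 26 (SAP 9.2.1 and 9.2.3), before the windows in Step 2 open.
- Between Weeks 26 and 48, a subject who stops study drug becomes a non-responder at later visits (SAP 9.1.2, applied in 9.3.1). These binary summaries are not ranked.
- Week 48 radiographic data are extrapolated linearly for subjects who stopped study drug prematurely (SAP 9.3.3; part of the condition is blacked out).
- Long-term efficacy is analyzed As Observed with no imputation (SAP 9.4), and that approach keeps data after discontinuation (SAP 9.1.2). Non-responder imputation does not operate there.

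**The case against.** The best defense is that the two sections can be obeyed together. Each is a trigger for stopping, and a site can stop at whichever is met first. On that reading the 21 and 30 days are outer limits on a hold, not an instruction to keep a subject whose infection is uncontrolled. Restart also depends on successful treatment, and the Investigator may stop drug in the subject's interest at any time.

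Much of this is right, and it limits the point. It does not remove it. The protocol nowhere says that the earlier trigger governs. Under that reading the longer limits and the restart provision in 6.1.7 would have no effect for the infections in the worked case. Discretion to stop does not settle two mandatory texts that disagree.

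A reader might also infer more than the documents support:

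- **That all treatment after Week 26 is in conflict.** Only infections uncontrolled at 2 weeks, later treated successfully, and with a hold in the stated windows are affected.
- **That the rules agree up to Week 26.** Only the number 14 agrees. An infection controlled on day 10 with dosing held for 15 days must stop under 6.1.7 but does not meet the 2-week limit in 5.4.1.
- **That 6.1.7 orders continuation for non-localized NMSC.** It only leaves such a case out of its mandatory stop.
- **That the infection conflict touches the main efficacy results or five years of response data.** Step 6 shows that it does not.

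**Conclusion.** The inconsistency is real and sits in the current text, but it is narrow.

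- **Serious infection:** a 7-day window in Weeks 26 to 48 (hold of 15 to 21 days) and a 16-day window afterwards (hold of 15 to 30 days), only for infections uncontrolled at 2 weeks and later treated successfully. The widths assume that both clocks start together.
- **NMSC:** non-localized cases only. The documents give no rate. Their only count is one subject with NMSC in the two Phase 2 studies (N = 575, Protocol 3.0), with the extent not stated.

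The main consequences are uneven handling of adverse events of special interest across several hundred centers, and uncertain counts of adverse-event discontinuations and of subjects not withdrawn when they should have been. For efficacy, the infection conflict can reach only the non-ranked binary summaries in Weeks 26 to 48 and the Week 48 radiographic extrapolation. The NMSC difference has no period limit, so timing alone does not exclude an earlier case, but nothing in the documents suggests an effect on the ranked endpoints.

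This should be corrected because these are mandatory safety stopping rules and wording alone can resolve it. No sample size, power or significance level depends on it.

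**What to change.** Reconcile the serious-infection and malignancy text in Protocol 5.4.1 with that in 6.1.7, so that the same serious-infection rule by study period and the same NMSC rule appear in both. For infection, the agreed text should say whether each time limit runs on control of the infection or on the interruption of dosing, and from when. The clinical team decides the rules; this review favors neither section.

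The cost is protocol wording in an amendment or a clarification letter. The SAP needs no change, since its analyses use discontinuation as recorded, and deviations under SAP 6.4 could then be judged against one text.
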